### **1.3 Dose Rationale**

The recommended dosing regimen in both the US and EU for adjunctive therapy with Lyrica® in adults with partial onset seizures ranges from 150 to 600 mg/day given BID or TID. The recommended dose range in adults is approximated by the 2.5 mg/kg/day to 10 mg/kg/day pregabalin dose range for pediatric subjects <60 kg in this study. This range of doses is anticipated to provide efficacy for the subjects enrolled and will characterize safety and tolerability of this dose range for pediatric subjects.

Doses in the range of 2.5 to 15 mg/kg/day were studied in pediatric subjects between 1 month and 16 years of age in Study A0081074 and serial blood samples were collected to assess the pharmacokinetics of pregabalin in the pediatric population. Data from Study A0081074 were compared with the adult data in a population pharmacokinetic analysis which showed that the relationship between creatinine clearance (CLcr) and pregabalin clearance (CL/F) was similar between both populations. Therefore, knowing a subject's CLcr value, the pregabalin oral clearance and thus pregabalin exposure can be estimated with a high degree of accuracy.

The noncompartmental and population pharmacokinetic analyses utilizing data from pediatric subjects from Study A0081074 indicated that for subjects with body weight  $\geq 30$  kg exposure equivalent to that observed in adults would be achieved when the pediatric subjects were dosed on a mg/kg/day basis. Due to higher clearance/kg in pediatric subjects with body weight  $< 30$  kg, a daily dose/kg 40% higher is needed to achieve exposure similar to that of adults or pediatric subjects weighing  $\geq 30$  kg. Thus, pediatric subjects with body weight  $\geq 30$  kg will initiate dosing at the daily dose of 2.5 mg/kg/day for a minimum of 1 week. Thereafter, dosing will be flexible, based on individual seizure response and tolerability. Doses may be adjusted up or down at clinic visits in increments no more than of 2.5 mg/kg/day. For pediatric subjects with body weight  $< 30$  kg, the daily dose will be adjusted by 40% to an initial daily dose of 3.5 mg/kg/day for a minimum of 1 week. Thereafter, dosing will be flexible, based on individual seizure response and tolerability. Doses may be adjusted up or down at clinic visits in increments of no more than 3.5 mg/kg/day.

Subjects  $< 4$  years of age at Visit 1 or participating from A0081042 will receive study medication TID in equally divided doses. Subjects who are  $\geq 4$  years of age at Visit 1 will receive study medication BID in equally divided doses. A TID dosing regimen accounts for a half life in youngest subjects shorter than in older pediatric and adult subjects. Subjects will maintain a BID or TID dosing regimen throughout study participation based on age at Visit 1 or past participation in A0081042 in order to avoid potential dosing errors/noncompliance related to regimen switch.

Adult subjects (17 to 65 years of age) who enroll in this study following participation in Study A0081105 will initiate dosing at 150 mg/day. Thereafter, dosing will be flexible, based on individual seizure response and tolerability. Doses may be adjusted up or down at clinic visits in increments of 150 mg/day.

## **2. STUDY OBJECTIVES AND ENDPOINTS**

### **2.1. Objectives**

- To evaluate the long-term safety and tolerability of pregabalin in pediatric subjects 1 month through 16 years of age with partial onset seizures and pediatric and adult subjects 5 to 65 years of age with (PGTC) seizures.

### **2.2. Endpoints**

#### **Safety Endpoints:**

- Adverse event (AE) data (occurrence, nature, intensity, and relationship to study drug).
- Physical and neurological examinations.
- Vital signs.
- Growth and development parameters (height, weight, Tanner stage).

- Clinical laboratory data (hematology, chemistry, urinalysis).
- Electrocardiograms (ECGs).
- 28-day seizure rate (number of seizures per 28 day period).
- Assessment of suicidal ideation and behavior.
- Cognitive assessment battery (POS pediatric subjects 4-16 years of age only).

### **3. STUDY DESIGN**

Study A0081106 is a 12 month, open-label, flexible dose, multicenter study to evaluate the tolerability and safety of pregabalin (administered BID in subjects  $\geq$ 4 years of age and TID in subjects  $<$ 4 years of age) as adjunctive therapy in pediatric subjects 1 month to 16 years of age with partial onset seizures and pediatric and adult subjects 5 to 65 years of age with (PGTC) seizures. Subjects who have completed the studies A0081041, A0081042, or A0081105 will be eligible for screening for this study. For subjects who have participated in, but did not complete Studies A0081041, A0081042, or A0081105, eligibility for Study A0081106 will be considered, after consultation with Study Clinician, on a case by case basis. A minimum of 4 weeks in the double-blind treatment phase of either Study A0081041 or Study A0081105 will be required for consideration of enrollment into Study A0081106.

Selected sites (within the United States only) that are not participating in studies A0081041 or A0081042 may screen and enroll pediatric subjects (1 month to 16 years of age) with partial onset seizures directly into Study A0081106 provided they meet the study inclusion/exclusion criteria. When subject enrollment for Studies A0081041 and A0081042 is complete, sites that were enrolling subjects in Studies A0081041 or A0081042 may screen and enroll pediatric subjects (1 month to 16 years of age) with partial onset seizures directly into Study A0081106 until enrollment into Study A0081106 is closed by Pfizer.

#### **3.1. Treatments and Visits**

[figure not shown]
The day of the last visit (completion of taper phase) of Studies A0081041, A0081042, and A0081105 is designated as Day 1 (Visit 1A) of this study. Baseline values for analysis of change in safety endpoints will be the assessments made prior to initiating double-blind dosing at Visit 1 of Studies A0081041, A0081042, or A0081105. For subjects directly entering Study A0081106 without participation in one of the studies above, baseline values for analysis of change in safety endpoints will be the assessments made at the first visit (Screening Visit 1B) of this study.

For pediatric subjects, pregabalin dosing will initiate at the daily dose of 2.5 mg/kg/day (subjects  $\geq$ 30 kg) or 3.5 mg/kg/day (subjects  $<$ 30 kg) at this visit. Adult subjects who enroll in this study following participation in Study A0081105 will initiate dosing at 150 mg/day. All seizures experienced will be self-recorded by the subject or recorded by their parents/legally acceptable representative as appropriate, in a daily seizure diary beginning at Visit 1 and subsequently throughout the entire study.

Subjects will return for the designated assessments of safety, tolerability, and drug accountability at Week 1 (Visit 2), Month 1 (Visit 3), Month 2 (Visit 4), Month 4 (Visit 5), Month 6 (Visit 6), Month 9 (Visit 7), Month 12/Early Termination (Visit 8), and Follow-up (Visit 9). Investigator site staff will contact the subject and/or parent/caregiver by telephone at least monthly between visits, to address questions, assess safety and adverse events, and ensure compliance with study directives.

At Visit 2 and subsequent visits thereafter, the investigator or designee will review seizure diary data and tolerability with the subject and may adjust the dose at his/her discretion. For pediatric subjects with body weight  $\geq 30$  kg (1 month to 16 years of age), doses may remain the same or be adjusted upward in increments of no more than 2.5 mg/kg/day to daily dose levels of 5.0, 7.5, or 10.0 mg/kg/day. For pediatric subjects with body weight  $< 30$  kg, doses may be adjusted in increments of no more than 3.5 mg/kg/day to daily dose levels of 7.0, 10.5, or 14.0 mg/kg/day. For adult subjects (17 to 65 years of age) doses may be adjusted in increments of 150 mg/day to daily dose levels of 300, 450, or 600 mg/day.

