### **Study Treatments:**

A0081106 study medication will be provided as pregabalin liquid oral solution or oral capsules. Subjects <4 years of age at Visit 1 or who are enrolling from A0081042 will receive study medication 3 times daily (TID) in equally divided doses. Subjects who are  $\geq 4$  years of age at Visit 1 will receive study medication twice daily (BID) in equally divided doses.

- All eligible pediatric subjects 1 month to 16 years and 11 months of age will take pregabalin in Study A0081106 at a dosage according to their body weight:
  - Pediatric subjects weighing  $\geq 30$  kg will begin pregabalin dosing at 2.5 mg/kg/day (maximum 150 mg/day). Subjects will remain at the starting dose for 8 days until Visit 2. Thereafter, dosing will be flexible based on individual seizure response and tolerability. Pediatric subjects may have their dose adjusted up or down at clinic visits in increments of no more than 2.5 mg/kg/day (maximum 150 mg/day) to daily dose levels of 5.0 (maximum 300 mg/day), 7.5 (maximum 450 mg/day), or 10.0 mg/kg/day (maximum 600 mg/day).
  - Pediatric subjects with body weight <30 kg will begin pregabalin dosing at 3.5 mg/kg/day until Visit 2. Thereafter, dosing will be flexible based on individual seizure response and tolerability. Pediatric subjects may have their dose adjusted up or down at clinic visits in increments of no more than 3.5 mg/kg/day to daily dose levels of 7.0, 10.5, or 14.0 mg/kg/day. This 40% higher dose per kg in pediatric subjects with body weight <30 kg is needed to achieve exposures similar to those of adults or pediatric subjects weighing  $\geq 30$  kg.
- All eligible adult subjects 17 to 65 years of age will begin dosing of pregabalin in Study A0081106 at the level of 150 mg/day. Subjects will remain at this dose for 8 days until Visit 2. Thereafter, dosing will be flexible based on individual seizure response and tolerability. Adult subjects may have their dose adjusted up or down at

clinic visits in increments of no more than 150 mg/day to dose levels of 300, 450, or 600 mg/day.

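### Protocol 3.1 lets doses for children of 30 kg or more stay the same or go up; the Summary, 1.3 and 5.1 allow up or down, so 3.1 needs correcting

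*Protocol*

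**What the plan says.** Protocol 3.1 describes dosing from Visit 2 onward. It opens with a general rule: the investigator or designee "will review seizure diary data and tolerability with the subject and may adjust the dose at his/her discretion". It then gives one sentence per group.

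- **Children of 30 kg or more:** "doses may remain the same or be adjusted upward in increments of no more than 2.5 mg/kg/day", to 5.0, 7.5 or 10.0 mg/kg/day.
- **Children under 30 kg:** "doses may be adjusted in increments of no more than 3.5 mg/kg/day to daily dose levels of 7.0, 10.5, or 14.0 mg/kg/day". No direction is stated.
- **Adults:** adjusted in steps of 150 mg/day to 300, 450 or 600 mg/day. No direction is stated.

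Elsewhere the protocol gives the rule for children of 30 kg or more without the upward limit.

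- **Protocol Summary, Study Treatments:** "Pediatric subjects may have their dose adjusted up or down at clinic visits in increments of no more than 2.5 mg/kg/day".
- **1.3 Dose Rationale:** "Doses may be adjusted up or down at clinic visits in increments no more than of 2.5 mg/kg/day".
- **5.1 Allocation to Treatment:** up or down, with the same 2.5 mg/kg/day maximum step.

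**The concern.** Within 3.1, only the sentence for children of 30 kg or more limits direction. The sentences for lighter children and for adults do not, so a careful reader could take the difference as deliberate. Read literally, it leaves dose reduction off the list of options for this group.

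Safety and tolerability are the study's only objective (Protocol 2.1), and lowering the dose is a basic response to poor tolerability. Section 1.2 reports that in Study A0081074 dizziness was seen only at 10.0 and 15.0 mg/kg/day, and 10.0 mg/kg/day is the top level here for children of 30 kg or more. That report is not split by weight, so it shows why dose reduction is relevant but does not measure a risk.

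Protocol 8.5 also makes an abnormal test finding reportable as an adverse event when it leads to a dosing change outside the adjustments that the protocol stipulates. The protocol should therefore say consistently which adjustments those are.

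**Working it through.** No calculation applies; the check is a comparison of text. Four sections (Summary, 1.3, 3.1, 5.1) each address three groups, which gives 4 × 3 = 12 statements.

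| Group | Summary | 1.3 | 3.1 | 5.1 |
|---|---|---|---|---|
| Children ≥30 kg | up or down | up or down | **upward** | up or down |
| Children <30 kg | up or down | up or down | none stated | none stated |
| Adults | up or down | up or down | none stated | none stated |

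The 1.3 entries for the other two groups read "Doses may be adjusted up or down at clinic visits in increments of no more than 3.5 mg/kg/day" for children under 30 kg and "Doses may be adjusted up or down at clinic visits in increments of 150 mg/day" for adults.

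**Count.**

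- 7 up or down + 1 upward + 4 with no direction = 12.
- Statements that name a direction: 7 + 1 = 8, of which 1 conflicts.
- For children of 30 kg or more alone, 1 of 4 conflicts.

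**Which side is in error.** Three sections agree against one for the same group and step size. The lead-in sentence in 3.1 ties adjustment to a tolerability review and sets no direction. Schedule of Activities footnote k and Protocol 6.3 (Visit 2) also base adjustment on seizure response and tolerability. No passage gives a reason to bar reductions in heavier children. The outlier is 3.1.

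**Visit 5 (separate point).** In the Schedule of Activities, footnote k, which allows dose adjustment if needed, is attached to the dispensing row at Visits 2, 3, 4, 5, 6 and 7: six visits. The matching line appears in the visit lists at 6.3, 6.4, 6.5, 6.9 and 6.12: five lists. It is absent from 6.7 (Visit 5), so 6 − 5 = 1 is missing.

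**The case against.** The strongest reply is that 3.1 does not forbid reduction. The verb is permissive, the word 'only' is absent, and the preceding sentence gives the investigator discretion at Visit 2 and every later visit. There is also a natural reading of the phrase. These children all start at 2.5 mg/kg/day, the lowest level, and stay there until Visit 2. At Visit 2 itself, staying the same or going up covers every available level.

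Sites would in any case look to 5.1 for dosing. Section 5.2.3 points there, and 5.1 has the rule right.

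The SAP adds little either way. SAP 2.1 repeats the lead-in sentence without the upward text, but it drops all three group-specific sentences, so its silence says little about direction. SAP 8.3.4 plans to summarise dose reductions due to adverse events, but for all subjects, so it would read the same if only the other groups could be reduced.

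Most of this stands as an argument about practical effect. It does not remove the conflict. The paragraph governs all visits from Visit 2 on, and after any increase the next decision may need to be a reduction. The group-specific sentence spells out the options and leaves that one out. The case for correction does not need the SAP: the three other protocol sections suffice.

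On Visit 5, the 6.7 list states nothing false, and Section 6 refers to the Schedule for each visit's procedures. That point would not merit comment alone.

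**Conclusion.** The concern holds. The phrase in Protocol 3.1 is inconsistent with the Summary, 1.3 and 5.1 and misstates the dosing rule for children of 30 kg or more. It is minor. The correct rule appears in three other places, the wording is permissive, and the practical effect is probably small. The study plans no statistical inference, and no endpoint, analysis set, sample size or derivation depends on the phrase. The number of subjects who might be affected cannot be estimated from the documents. The conclusion assumes that the sponsor meant one rule for this group throughout, which the text supports and nothing in it contradicts. The missing Visit 5 line is a matter of conformity only.

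**What to change.** In Protocol 3.1, in the sentence on children of 30 kg or more, replace 'adjusted upward' with 'adjusted up or down'. As a conforming edit, add to the Visit 5 list in 6.7 the same if-needed dose-adjustment line that the Visit 3, 4, 6 and 7 lists carry, to match Schedule footnote k.

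The cost is one phrase and one bullet in the next amendment, with no new data, visits or SAP change.

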**Figure 1. Study Design Schematic**

Subjects who discontinue early and those who complete the study and do not continue treatment with pregabalin are recommended to taper off of study medication (see below for recommended tapering schedule), and will return for Visit 9 when the taper is completed.

For pediatric subjects  $\geq 30$  kg who taper off of pregabalin, the following schedule is recommended:

- Subjects receiving a dose of 10.0 mg/kg/day should receive 5.0 mg/kg/day for 4 days, then 2.5 mg/kg/day for 3 days, then discontinue study medication.
- Subjects receiving a dose of 7.5 mg/kg/day should receive 5.0 mg/kg/day for 4 days, then 2.5 mg/kg/day for 3 days, then discontinue study medication.
- Subjects receiving a dose of 5.0 mg/kg/day should receive 2.5 mg/kg/day for 7 days, and then discontinue study medication.
- Subjects receiving a dose of 2.5 mg/kg/day may discontinue study medication without any taper.

**Table 1. End-of-Treatment Taper Schedule for Pediatric Subjects >30 kg**

Day  / Total Daily Dose	Day 1	Day 2	Day 3	Day 4	Day 5	Day 6	Day 7/ Follow up
10.0 mg/kg/day	5.0	5.0	5.0	5.0	2.5	2.5	2.5
7.5 mg/kg/day	5.0	5.0	5.0	5.0	2.5	2.5	2.5
5.0 mg/kg/day	2.5	2.5	2.5	2.5	2.5	2.5	2.5
2.5 mg/kg/day	0	0	0	0	0	0	0

1. Days 1-7 post-Month 12/Early Termination visit.

For pediatric subjects <30 kg who taper off of pregabalin, the following schedule is recommended:

- Subjects receiving a dose of 14.0 mg/kg/day should receive 7.0 mg/kg/day for 4 days, then 3.5 mg/kg/day for 3 days, then discontinue study medication.
- Subjects receiving a dose of 10.5 mg/kg/day should receive 7.0 mg/kg/day for 4 days, then 3.5 mg/kg/day for 3 days, then discontinue study medication.
- Subjects receiving a dose of 7.0 mg/kg/day should receive 3.5 mg/kg/day for 7 days, and then discontinue study medication.
- Subjects receiving a dose of 3.5 mg/kg/day may discontinue study medication without any taper.

**Table 2. End-of-Treatment Taper Schedule for Pediatric Subjects <30 kg**

Day  / Total Daily Dose	Day 1	Day 2	Day 3	Day 4	Day 5	Day 6	Day 7/ Follow up
14.0 mg/kg/day	7.0	7.0	7.0	7.0	3.5	3.5	3.5
10.5 mg/kg/day	7.0	7.0	7.0	7.0	3.5	3.5	3.5
7.0 mg/kg/day	3.5	3.5	3.5	3.5	3.5	3.5	3.5
3.5 mg/kg/day	0	0	0	0	0	0	0

1. Days 1-7 post-Month 12/Early Termination visit.

For adult subjects (17 to 65 years of age) who taper off of pregabalin, the following schedule is recommended:

- Subjects receiving a dose of 600 mg/day should receive 300 mg/day for 4 days, then 150 mg/day for 3 days, then discontinue study medication.
- Subjects receiving a dose of 450 mg/day should receive 300 mg/day for 4 days, then 150 mg/day for 3 days, then discontinue study medication.
- Subjects receiving a dose of 300 mg/day should receive 150 mg/day for 7 days, and then discontinue study medication.
- Subjects receiving a dose of 150 mg/day may discontinue study medication without any taper.

**Table 3. End-of-Treatment Taper Schedule for Adult Subjects**

Day  / Total Daily Dose	Day 1	Day 2	Day 3	Day 4	Day 5	Day 6	Day 7/ Follow up
600 mg/day	300	300	300	300	150	150	150
450 mg/day	300	300	300	300	150	150	150
300 mg/day	150	150	150	150	150	150	150
150 mg/day	0	0	0	0	0	0	0

1. Days 1-7 post-Month 12/Early Termination visit.

#### **4. SUBJECT SELECTION**

This study can fulfill its objectives only if appropriate subjects are enrolled. The following eligibility criteria are designed to select subjects for whom protocol treatment is considered appropriate. All relevant medical and non-medical conditions should be taken into consideration when deciding whether this protocol is suitable for a particular subject.

##### **4.1. Inclusion Criteria for Subjects who have Participated in Studies A0081041, A0081042, or A0081105**

Subject eligibility should be reviewed and documented by an appropriately qualified member of the investigator's study team before subjects are included in the study. Subjects must meet all of the following inclusion criteria to be eligible for enrollment into the study:

1. Evidence of a personally signed and dated informed consent document indicating that the subject (or a legally acceptable representative) has been informed of all pertinent aspects of Study A0081106. When there are 2 parents or 2 legally acceptable representatives, consent should be obtained from both of the child's parents/legal representatives if present at the meeting where the informed consent document is signed. Subject to local regulations whenever the minor is able to give assent, the minor's assent must be obtained.
2. Subjects and/or parents/legally acceptable representative who are willing and able to comply with scheduled visits, treatment plan, laboratory tests, and other study procedures.

090177e1929ceac9\Approved\Approved On: 17-Jan-2020 08:05 (GMT)

3. Male and female subjects who have participated in and completed, or participated in Studies A0081041, A0081042, or A0081105. For subjects who have participated in, but did not complete Studies A0081041, A0081042, or A0081105, eligibility for Study A0081106 will be reviewed with a member of the Pfizer study team to determine further eligibility. Subjects are required to have completed a minimum of 4 weeks of double-blind treatment in Studies A0081041 or A0081105 to be considered potentially eligible for Study A0081106.
4. Male and female epilepsy subjects who have participated in either Study A0081041 or Study A0081042, 1 month to 16 years of age inclusive on the date of the Screening Visit with diagnosis of epilepsy with seizures classified as simple partial, complex partial or partial becoming secondarily generalized, according to the International League Against Epilepsy (ILAE 2010^3) (See [Appendix 1](#) for additional seizure types). The diagnosis must be established by:
  - Subject's history (eg, description of seizures excluding confounding disorders such as pseudoseizures, syncope etc) family history and neurological exam.
  - Subjects must have had a contrast enhanced computed tomography (CT) or magnetic resonance imaging (MRI) scan of the brain and electroencephalogram (EEG) testing prior to Study A0081041 or Study A0081042. Results must have been consistent with the diagnosis of focal-onset epilepsy and must have demonstrated that no abnormality was likely to be progressive.
5. Male and female subjects 5-65 years of age who have participated in Study A0081105 with a diagnosis of epilepsy (ILAE 2010^3) with PGTC seizures and who continue to satisfy seizure related inclusion criteria for that study (see Protocol A0081105). Subjects who have participated in study A0081105 and who reach the age limit of 66 years of age will still be allowed to enter this study.
6. Currently receiving a stable dose of 1 to 3 antiepileptic drugs at Visit 1. Benzodiazepine medication used on a regular basis will be considered 1 of the concurrent antiepileptic treatments. The vagus nerve stimulator (VNS) is allowed and considered 1 of the 3 antiepileptic treatments.
7. A 12-lead ECG at (the last visit of Studies A0081041, A0081042, A0081105) without significant abnormal findings.

